8.3 Exploratory Analysis

Exploratory analyses will be performed to compare immunogenicity endpoints between specified study groups. All exploratory analyses will be performed by treatment received based on IPPS. The following group-wise (targeted group vs. reference group) comparisons will be performed for GMT and SPR of HAI antibody responses:

• For strain A/gyrfalcon/Washington/41088-6/2014 H5N8 (Seqirus) on Day 43:

Study Group A vs. Study Group E

Study Group B vs. Study Group E

Study Group C vs. Study Group E

Study Group D vs. Study Group E

Study Group F vs. Study Group E

Study Group G vs. Study Group K

Study Group H vs. Study Group K

Study Group I vs. Study Group K

Study Group J vs. Study Group K

Study Group L vs. Study Group K

 For strain A/barheaded goose/Qinghai Lake/1A/2005 (H5N1) (Sanofi Pasteur) on Day 163: Study Group E vs. Study Group F

Study Group K vs. Study Group L

The logarithms of HAI antibody titers will be compared by two-sided Student's t-test between above specified study groups. Geometric mean ratio estimate will also be presented for each pair of group comparison with corresponding asymptotic 95% CIs and p-values based on two sample t-test.

The difference in proportions (SPR for targeted group-SPR for reference group) between the above specified study groups will be presented along with corresponding asymptotic 95% CIs and p-values based on Chi-square test.

Based on actual results, additional exploratory study group comparisons may be performed.

9 Safety Analysis

All safety evaluations will be performed using the Safety Set.

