3.3 Study Groups

This is a double-blinded study with 12 study groups (i.e. treatment groups). The summary will be based on each of the 2 adjuvants (summary table includes 6 treatment arms in one page for each adjuvant). For subjects missed the second and/or third vaccinations, the randomized treatment groups will be used for summarizing these subjects. For a complete list of study groups and corresponding vaccination and adjuvants schemes refer to Table 3-1.

4 General Statistical Considerations

For continuous variables, descriptive statistics will typically include the number of subjects, mean, standard deviation (SD), 25th percentile (Q1), median, 75th percentile (Q3), minimum, and maximum. For categorical variables, descriptive statistics will typically include the number and percentage of subjects in each category. Unless otherwise noted, data from all sites will be combined in the computation of these descriptive statistics.

In statistical summaries, mean, median, Q1, and Q3 will be displayed to one more decimal place than the original value; minimum and maximum will keep the same number of decimal places as the original value; standard deviation will be displayed to two more decimal places than the original value; percentages will generally be reported to one decimal place.

Computation for all the results will be performed using SAS[®] version 9.3 or higher computer software package.

Baseline

Unless otherwise specified, baseline will be defined as the last non-missing measurement prior to the first vaccination.

Study Day

Study Day will be calculated as event/assessment date - first dose date of IP if the assessment occurs before the first dose; Study Day will be calculated as event/assessment date - first dose date of IP + 1 Day if the assessment occurs on or after the first dose.

Subject Counts in Table Headers

The subject counts (N's) for each study group in the table header will equal the number of subjects who receive the actual treatment as the study group displayed unless otherwise specified. All other subjects who receive any vaccination different from group A-L regimen will be included in the listings and overall column (per adjuvant) if available. Overall column will be included in the tables based on randomized treatment only.

Safety Data Reporting Periods

The safety data reporting periods are shown in Table 4-1.

of Event	Collection Period: Study Days
ited AEs	Days 1-8 Post each vaccination

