4.2.2 Stratification

Randomization is stratified by site to balance treatment assignments over the course of the trial within each site.

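### The regimen comparisons in SAP 8.3 ignore the site stratification and leave the variance assumption to convention; the cost is a small loss of precision, not bias

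*SAP*

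**What the plan says.** SAP 8.3 lists 12 pairwise comparisons of HAI responses. Ten are for the gf/WA strain at Day 43 (A, B, C, D and F against E; G, H, I, J and L against K). Two are for bhg/QL at Day 163 (E against F, K against L).

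- Titres: "The logarithms of HAI antibody titers will be compared by two-sided" Student's t-test. The geometric mean ratio carries "corresponding asymptotic 95% CIs and p-values based on two sample t-test".
- SPR: the difference in proportions carries "corresponding asymptotic 95% CIs and p-values based on Chi-square test".
- Analysis set: "All exploratory analyses will be performed by treatment received based on IPPS".

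Neither 8.3 nor any other section names a covariate, a stratified test or an unequal-variance option. SAP 4.2.2 states: "Randomization is stratified by site to balance treatment assignments over the course of the trial within each site". For descriptive summaries, SAP Section 4 says: "Unless otherwise noted, data from all sites will be combined in the computation of these descriptive statistics". A Day 1 HAI titre is taken in every group (Protocol 6.3, SAP 8.2).

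**The concern.** Stratifying by site removes between-site differences from the true sampling error of a group contrast. An analysis that omits site leaves those differences in the estimated error, so the standard error is overstated whenever site matters.

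Student's t-test conventionally pools the two variances. The SAP does not use the word pooled, but nor does it name an alternative. Equal variances cannot be presumed for gf/WA at Day 43. Groups E and K have received only dk/BANG by then, so many of their titres may sit at the half-detection-limit value, while every comparator has received gf/WA at least once.

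The primary and secondary analyses are descriptive by group. The 8.3 comparisons are therefore the only planned between-group estimates with intervals and p-values, on questions that the Protocol Introduction says the study will address (choice and sequence of antigens). At stake is how precise and well calibrated those intervals are.

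**Working it through.** **The plan's own figures.** SAP Table 4-3 reproduces exactly: single-group power against 70% SPR with cut-offs 49/60 and 93/120 gives 98.5, 81.9 and 44.9% at N=60, and >99.9, 99.0 and 79.0% at N=120. Table 4-2 reproduces to within 0.1 point. Neither bears on 8.3; the documents give no SD, detectable ratio or power for the between-group comparisons.

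**Inputs.** From the documents: 60 per group, equal allocation, site stratification, two-sided 95% intervals. Assumed: 6 or 10 equal-sized sites (the current text says only that there are multiple sites), site intraclass correlation (ICC), SD ratios and per-protocol group sizes.

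**1. Site.** If site explains a share s of the variance, adjusting for it narrows the SE by 1 − √(1 − s): 1.0% at s = 0.02, 2.5% at 0.05, 5.1% at 0.10. Power is benchmarked at the difference with 80% unadjusted power: (1.960 + 0.842) × √(2/60) = 0.511 SD. Simulation, 20,000 trials per row:

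| Sites | ICC | Type I error, unadjusted | Type I error, with site | Power, unadjusted | Power, with site |
|---|---|---|---|---|---|
| 6 | 0.02 | 4.9% | 5.1% | 79.8% | 80.3% |
| 6 | 0.05 | 4.3% | 4.9% | 80.4% | 81.8% |
| 6 | 0.10 | 4.1% | 4.9% | 81.6% | 83.9% |
| 6 | 0.20 | 3.2% | 4.9% | 82.5% | 87.0% |
| 10 | 0.05 | 4.4% | 4.9% | 79.7% | 81.0% |
| 10 | 0.10 | 3.9% | 4.9% | 80.7% | 83.3% |

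At ICC 0.05 to 0.10 the loss is 1.3 to 2.5 power points.

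**2. Pooled variance.** With equal n the pooled and Welch SEs are identical, and the simulated pooled error at SD ratio 3 is 5.1 to 5.2%. With unequal n the direction depends on which group is more variable. For n = 58 and 46:

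- Larger group more variable (SD 3 and 1). True variance of the difference: 9/58 + 1/46 = 0.177. Pooled: [(57×9 + 45×1)/102] × (1/58 + 1/46) = 0.213. The SE is overstated by √(0.213/0.177) − 1, about 10%. Simulated error: 3.3% pooled, 5.0% Welch.
- Smaller group more variable (SD 1 and 3). True: 1/58 + 9/46 = 0.213. Pooled: [(57×1 + 45×9)/102] × (1/58 + 1/46) = 0.177. The SE is understated by about 9%. Simulated error: 7.6% pooled, 5.0% Welch.

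**3. Which direction the design suggests.** Under SAP 4.3.5, E, F, K and L enter the per-protocol set only with all three doses and an in-window Day 163 sample. A-D and G-J need two doses and an in-window Day 43 sample. Eight of the 12 pairs (A-D against E, G-J against K) therefore set a two-dose group against a three-dose group that is likely to be smaller. If that smaller group is also the one near the assay floor, the first case applies. The other four pairs (F-E, L-K, E-F, K-L) join groups under identical rules, so similar n is expected.

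**4. Day 1 titre.** Exclusion 18 removes people with prior H5 vaccination or infection, and SAP Section 8 sets undetectable titres to one constant. If 2 to 10% are detectable at Day 1 (assumed), R² is about 0.01 to 0.12, and power at the same benchmark is 80 to 85%. The low end is the more plausible.

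**The case against.** The best defence is that the analyses are exploratory. SAP Section 1 plans no formal comparison for the primary and secondary objectives, Protocol 7.7 disclaims formal significance testing, and no alpha is stated, so no decision depends on an exact error rate. The group-wise rates and titres with 95% intervals in SAP 8.1 and 8.2 let a reader compare regimens informally. All of this stands and limits the weight of the point. It does not explain leaving out a stratification factor that is already recorded.

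Adjustment is also not free of difficulty. With 60 per group over an unstated number of sites, some strata may be small, and if E and K have almost no seroprotected subjects some strata may have no events. This stands too, and is why the fix needs a pooling rule.

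A reader might infer that the planned t-test inflates false positives, as the 7.6% suggests. The documents do not support that. It requires the smaller group to be the more variable one, whereas floor-level titres in E and K, together with the stricter per-protocol rule for those groups, point the other way. A reader might also expect a large gain from the Day 1 titre; exclusion 18 and the constant for undetectable values make a small one more likely.

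**Conclusion.** The point holds as a minor one. SAP 8.3 leaves out the stratification factor and does not say how unequal variances are handled. Omitting site widens the intervals slightly and makes the tests mildly conservative; it does not bias the comparison of the groups as randomised. The effect of pooling is nil at equal n and could go either way otherwise; in the likelier direction it is again conservative. Unequal-variance standard errors hold about 5% in both directions.

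The sizes rest on assumed ICCs, site numbers, SD ratios and per-protocol attrition. The reading of Student's t-test as pooled is conventional rather than stated. No primary or secondary result changes.

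**What to change.** Amend SAP 8.3 as follows:

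- For each listed pair, fit a linear model to log HAI titre with group and site. Add log Day 1 titre for strains where it varies. Use unequal-variance or robust standard errors, and report the geometric mean ratio with its 95% interval.
- For SPR, report a Mantel-Haenszel difference stratified by site.
- Fix a numerical threshold for pooling small or no-event sites before unblinding.
- Keep the unadjusted t-test and chi-square results as sensitivity analyses.

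The cost is SAP wording and some programming; no new data are needed. The one real burden is the pooling rule, which must be set in advance so that it does not become a choice made after seeing results.

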9.1 Adverse Events

An AE is defined as any untoward medical occurrence in a subject enrolled into this study regardless of its causal relationship to IP.

An SAE is defined as any event that results in death, is immediately life threatening, requires inpatient hospitalization or prolongation of existing hospitalization, results in persistent or significant disability/incapacity, or is a congenital anomaly/birth defect. Important medical events that may not result in death, be life threatening, or require hospitalization may be considered SAEs when, based upon appropriate medical judgment, they may jeopardize the

subject or may require medical or surgical intervention to prevent one of the outcomes listed in this definition.

Medically attended AEs are defined as AEs with medically attended visits, including hospital, emergency room, urgent care clinic, or other visits to or from medical personnel (medical doctor, physician assistant, nurse practitioner) for any reason.

Potentially immune-mediated medical conditions are considered adverse events of special interest. The PIMMCs of concern for this study are detailed in Appendix 2, Section 14.2.

AEs are categorized into 'Solicited Local AEs', 'Solicited Systemic AEs', and 'Unsolicited AEs' for AE type. Solicited Local AEs will include local reactions at the injection site with an onset within the 8 days after each vaccination, such as erythema/redness, induration/swelling, and pain. Solicited Systemic AEs will include systemic reactions with an onset within the 8 days after each vaccination, such as fever, myalgia, arthralgia, fatigue, headache, nausea, vomiting, diarrhea, and chills. All solicited local and systemic reactions will be considered as related to IP by the investigator. All other AEs which are not solicited are considered unsolicited.

Days of onset for unsolicited AEs are categorized into '1-8 Days' and '>8 Days' from each IP administration.

Adverse events will be coded using the Medical Dictionary for Regulatory Activities (MedDRA)[®], which provides the primary system organ class (SOC) and preferred term (PT) information.

All AEs reported after the first dose of IP will be summarized in tables. AEs within 21 days of each dose of IP, and before the date and time of the next dose of IP (if applicable) will be summarized in tables based on each dose only (Dose 1, 2 for Groups A-D, G-J; Dose 1, 2, 3 for Group E, F, K and L). When the time of an AE is missing and the AE start date is on the date of vaccination, then that AE will be considered as happening after the corresponding dose of IP.

All AEs will be summarized by presenting the number and percentage of subjects having any AEs and having each individual adverse event based on SOC and PT, and PT only. At each level of subject summarization, a subject is counted once if the subject reported one or more events. Percentages will be calculated out of the number of subjects as treated per study group in the Safety Set. For the dose-specific AE summaries, percentages will be calculated out of the number of subjects as treated per study group corresponding to Dose 1, Dose 2 or Dose 3.

Unless otherwise stated, AEs will be sorted in descending order by frequency of SOC and PT.

The following summaries, based on Dose 1 only, Dose 2 only, and both Dose 1 and Dose 2 for Groups A-D, G-J and Dose 1 only, Dose 2 only, Dose 3 only, and all Dose 1, Dose 2 and Dose 3 for Groups E, F, K and L will be provided:

- Overview summary of the number and percentage of subjects with any AE, SAE, AE related to IP, AE leading to study withdrawal, AE leading to death, solicited local AE, severe solicited local AE, solicited systemic AE, severe solicited systemic AE, MAAE, PIMMC, unsolicited AE, severe unsolicited AE, and unsolicited AE related to IP
- All AEs by SOC and PT
- All AEs by AE Type and PT
- All AEs by SOC, PT and Severity

- All AEs by SOC, PT and Relationship
- All unsolicited AEs by SOC, PT and Day of Onset

The following summaries with 95% exact CIs using Clopper Pearson method, based on events recorded during the 8 days post each vaccination will be provided as the analysis of primary safety endpoint:

- Solicited Local AEs by Severity
- Solicited Systemic AEs by Severity

All MAAEs and PIMMCs after the first dose of IP will be summarized in a table by SOC, PT and Severity.

In all by-severity summaries, the severity that will be presented represents the greatest severity captured in the eCRF if a subject reported multiple occurrences of the same AE. The possible severities include "Mild", "Moderate" and "Severe". The missing severity will be imputed as "Severe".

In all by-relationship summaries, the relationship that will be presented represents the greatest relatedness captured in the eCRF if a subject reported multiple occurrences of the same AE. The possible relationship includes "Related" and "Unrelated". The missing relationship will be imputed as "Related".

All AEs will be included in a data listing containing all subject-level data collected in the eCRF. All SAEs, all AEs leading to study withdrawal, MAAEs, PIMMCs and severe AEs will be listed separately.

A listing of SAEs and MAAEs, including a subset of specific PIMMCs for 12 months after the last dose of study vaccine will be presented in the addendum to the CSR once the study is complete.

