6.2.5.2 Solicited Local and Systemic Reactogenicity Symptoms

All subjects will record solicited local and systemic reactions and other unsolicited symptoms/complaints, including start and stop dates, on an 8-day diary card following each vaccination. The investigator or his/her designee will review the information from the diary card or from memory with the subject at each visit and grade reactogenicity using a standard toxicity grade (Appendix 3, Section 12.3). The diary card will be collected from the subjects and stored as a source document.

- Solicited local reactions at the injection site will include erythema/redness, induration/swelling, and pain.
- Solicited systemic reactions will include fever, myalgia, arthralgia, fatigue, headache, nausea, vomiting, diarrhea, and chills.

The above solicited local and systemic reactions will be recorded including start and stop dates, worst daily grade, any treatment required, and action taken. The investigator will assess if solicited local and systemic reactions will be considered as related to IP according to Section 6.2.5.6. The severity of local and systemic reactions will be graded using the FDA Toxicity Grading Scale for Healthy Adult and Adolescent Volunteers Enrolled in Preventive Vaccine Clinical Trials (Appendix 3, Section 12.3).

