V	Solicited AEs Unsolicited AEs ^a	Dose 3	Postvaccination Days 1-8	Days 142-149	Groups E, F, K, L	
VI	Unsolicited AEs ^a	Dose 3	Postvaccination Days 9-21	Days 150-163	Groups E, F, K, L	
NA	SAEs, MAAEs, and PIMMCs		Entire study period ^b		All	
NA	Pregnancies		Entire study period ^c		All	

Abbreviations: AE, adverse event; MAAE, medically attended adverse event; PIMMC, potentially immune-mediated medical condition; SAE, serious adverse event.

Unsolicited AEs will be collected through the end of the study visit window for each AE collection period (ie, 21 days after each vaccination ± 3 -day window = 21 ± 3 days).

b The entire study period is from the time a subject receives the first study injection through the end-of-study visit. If the investigator becomes aware of any related SAE or related MAAE after exit from or completion of the study, he or she is obligated to report this event.

с Pregnancies that occur during a subject's participation in the study will be followed until resolution and 2 weeks after live birth even if the pregnancy ends after the end-of-study visit.

6.2.5.4 **Reporting Adverse Events**

All AEs reported or observed during the study will be recorded on the AE page in the eCRF. Information to be collected includes event term, time of onset, investigator-specified assessment of severity and relationship to IP, time of resolution of the event, seriousness, any required treatment or evaluations, and outcome. Adverse events resulting from concurrent illnesses, reactions to concurrent illnesses (unless judged by the investigator to be expected for the subject's underlying condition), reactions to concurrent medications, or progression of disease states must also be reported. All AEs will be followed to adequate resolution or stabilization. The latest version of the Medical Dictionary for Regulatory Activities

```
BARDA CSNH5 Influenza Vaccine With Either AS03 or MF59Protocol: BP-I-16-005 Version 2.026 February 2018(MedDRA) at the time of study startup will be used to code all AEs. Additional detailsregarding reporting of local and systemic reactions are provided in Section 6.2.5.2.
```

Any medical condition that is present at the time that the subject is screened but does not deteriorate should not be reported as an AE. However, if it deteriorates beyond what is expected for that condition at any time during the study, it should be recorded as an AE.

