6.2.5.5 Assessment of Severity

The severity of an AE refers to the extent to which an AE affects the subject's daily activities. All solicited AEs will be graded according to the FDA Toxicity Grading Scale (Appendix 3, Section 12.3) and entered into the AE reporting page. Grade 1-3 hematology or serum chemistry values determined by the investigator to be clinically significant will be entered into the AE reporting page. An FDA toxicity Grade 2 (moderate) or greater (ie, $\geq 2.6 \times$ ULN; see Appendix 3, Section 12.3) ALT and/or AST elevation (regardless of investigator-assessed clinical significance) will be entered into the AE reporting page, and the grading will be consistent with the FDA toxicity score. All Grade 4 laboratory findings are considered AEs regardless of the investigator's determination of clinical significance and should also be entered using the FDA toxicity score for severity. In all other cases, the severity of each AE will be rated as mild, moderate, or severe using the following criteria:

Mild:	An event usually transient in nature and generally not interfering with
	normal activities.
Moderate:	An AE that is sufficiently discomforting to interfere with normal
	activities.
Severe:	An AE that is incapacitating and/or prevents normal activities.

Changes in the intensity of an AE should be documented to allow an assessment of the duration of the event at each level of intensity to be performed. Adverse events characterized as intermittent do not require documentation of onset and duration of each episode. The severity of solicited AEs will be classified.

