10.1.2 Principal Investigator

The principal investigator has a personal responsibility to closely monitor study subjects and an inherent authority to take whatever measures necessary to ensure their safety. The principal investigator has the authority to terminate, suspend, or require changes to a clinical study for safety concerns and may delay an individual's study IP administration if the principal investigator has some suspicion that the study vaccine might place a subject at significant risk. Where specified, responsibilities of the principal investigator may be delegated to a medically qualified team member (designee). The principal investigator or designee determines severity and causality with respect to the study IP for each AE.

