11.1 Study Pausing Rules

Study pausing rules will be monitored throughout the study by the medical monitor. The sponsor will pause study enrollment and study vaccine administration and the IDMC will review unblinded safety data if any of the following are met:

- Occurrence of one or more SAE(s), MAAE(s), or PIMMC(s) judged to be related to IP; OR
- Any potentially life-threatening AE judged to be related to IP (An adverse event or suspected adverse reaction is considered "life-threatening" if, in the view of either the investigator or sponsor, its occurrence places the patient or subject at immediate risk of death. It does not include an adverse event or suspected adverse reaction that, had it occurred in a more severe form, might have caused death); OR
- A death, if judged to be related to IP; OR
- Anaphylaxis or bronchospasm within 4 hours of injection judged to be related to IP; OR
- 10% of vaccinated subjects at a given vaccination time point when at least 50% of subjects in that group have been vaccinated experience the same or similar systemic or local Grade 3 (toxicity scoring) or higher event; OR
- A pattern of significant symptoms, physical findings, or laboratory abnormalities that, although individually minor, collectively represent a safety concern in the opinion of the investigator or the medical monitor.

If any of the above rules is met, the study will be paused. An unblinded safety report will be submitted to IDMC for review. The safety report will include summary of study disposition and demographic information for all randomized subjects and adverse events for safety set. Also, listing of protocol deviations, all adverse events, vaccination site examination for subjects with severe reaction, significant physical findings, vital signs and laboratory results for subjects with toxicity grade 3 or above will be provided to IDMC for review.

12 References

- 1. Afluria, Influenza Virus Vaccine [package insert]. CSL Limited (Australia); 2010.
- 2. Fluzone Quadrivalent (Influenza Vaccine) [package insert]. Sanofi Pasteur Inc. Swiftwater (PA); 2016.
- 3. Flucelvax Quadrivalent (Influenza Vaccine) [package insert]. Seqirus, Inc. Holly Springs (NC); 2016.
- 4. Influenza A (H5N1) Virus Monovalent Vaccine, Adjuvanted; Emulsion for Intramuscular Injection [package insert]. Quebec City (QC, Canada); GlaxoSmithKline 2013.
- 5. SAS Institute Inc. SAS® Procedures Guide, Version 9.3. Cary, NC: SAS Institute Inc. 2008.

13 Analyses Deviated From Protocol

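### SAP 9.1 calls every solicited reaction vaccine-related, against Protocol 6.2.5.2 and the SAP's own eCRF rule, so two related-AE outputs have no single definition

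*SAP*

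**What the plan says.** Protocol 6.2.5.2, on solicited reactions: "The investigator will assess if solicited local and systemic reactions will be considered as related to IP according to Section 6.2.5.6". Section 6.2.5.6 of the protocol offers two outcomes, Unrelated and Related, according to whether there is a reasonable possibility that IP caused the event. Protocol 10.1.2 assigns the decision generally: "The principal investigator or designee determines severity and causality with respect to the study IP for each AE".

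The judgement is also collected. Protocol 6.2.5.5 states: "All solicited AEs will be graded according to the FDA Toxicity Grading Scale (Appendix 3, Section 12.3) and entered into the AE reporting page". Protocol 6.2.5.4 lists, among the items recorded on the AE page, the "investigator-specified assessment of severity and relationship to IP".

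SAP 9.1, where it defines the AE types, says: "All solicited local and systemic reactions will be considered as related to IP by the investigator". Further on, the same section plans an overview that includes a row for AEs related to IP and a table titled "All AEs by SOC, PT and Relationship", each by dose and across doses. For by-relationship summaries it then says that "the relationship that will be presented represents the greatest relatedness captured in the eCRF" when a subject has several occurrences of the same AE. It names Related and Unrelated as the possible values, imputes only a missing relationship as Related, and makes no exception for solicited AEs.

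SAP Section 13, on departures from the protocol, lists two omitted exploratory immunogenicity objectives and nothing about relatedness.

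**The concern.** The same variable has two rules. The protocol treats the relatedness of a solicited reaction as a judgement with two possible answers; one sentence of the SAP fixes the answer. A second rule in the same SAP section goes back to the recorded judgement. A programmer who meets a solicited fever, headache or diarrhea that the investigator marked Unrelated, for example because of an intercurrent infection, cannot satisfy both SAP statements.

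At stake is what the related-AE figures in the study report mean. Under the blanket sentence, the share of subjects with a related AE can never be lower than the share with any solicited reaction, whatever the investigators recorded. Under the eCRF rule it can be lower. A reader of the report could not tell which was applied.

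**Working it through.** The plan gives no figure for relatedness, so there is nothing to reproduce. The check is a comparison of texts, followed by an illustration of scale.

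**1. One record under each rule.** Take a solicited reaction that the investigator marks Unrelated on the AE page.

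| Source | Value to tabulate |
|---|---|
| Protocol 6.2.5.2 with 6.2.5.6 and 10.1.2 | Unrelated (investigator's assessment) |
| SAP 9.1, AE-type paragraph | Related (all solicited reactions) |
| SAP 9.1, by-relationship paragraph | Unrelated (value in the eCRF; only missing values become Related) |

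For a reaction marked Related, or with relationship missing, the two SAP rules agree. The conflict is confined to solicited reactions recorded as Unrelated.

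**2. Is it a version effect?** The SAP is based on protocol version 1.2, and the current protocol is 2.0. The change logs for versions 1.2 and 2.0 show no change to the sentence in Protocol 6.2.5.2. Unhighlighted editorial changes are possible, but nothing in the logs explains the difference.

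**3. Which outputs are exposed?**

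- Exposed: the overview row for AEs related to IP, and the table of all AEs by SOC, PT and relationship. Both pool solicited and unsolicited events. The eCRF rule is written for by-relationship summaries, so the overview row has no explicit rule of its own.
- Not exposed: the primary safety tables (solicited local and systemic AEs by severity, with Clopper-Pearson intervals), the overview row for related unsolicited AEs, and the table of unsolicited AEs by day of onset.
- The listing of all AEs carries the subject-level eCRF data, so the recorded judgement stays visible there.

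**4. Scale, by illustration only.** The documents give no rate of solicited reactions and no rate of reactions judged unrelated. Assume, per group of 60 (Protocol 7.4):

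- s = share of subjects with at least one solicited reaction, 50% to 90%
- u = share of those whose solicited reactions were all judged unrelated, 0 to 20%
- r = share with a related unsolicited AE, 10%, independent of the rest

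Share with any related AE:

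- blanket rule: 1 − (1 − s)(1 − r)
- eCRF rule: 1 − (1 − s(1 − u))(1 − r)
- difference: s × u × (1 − r)

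| s | Blanket rule, subjects of 60 | eCRF rule, u = 0 to u = 20% | Difference, percentage points |
|---|---|---|---|
| 50% | 33.0 | 33.0 to 27.6 | 0 to 9.0 |
| 70% | 43.8 | 43.8 to 36.2 | 0 to 12.6 |
| 90% | 54.6 | 54.6 to 44.9 | 0 to 16.2 |

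For the largest entry: 0.90 × 0.20 × 0.90 = 0.162. At u = 0 the difference vanishes for every s.

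**The case against.** The strongest reply is that the blanket sentence states no recoding step. It says the reactions will be considered related by the investigator, which can be read as a description of what sites are expected to record. The operative table rule is then the eCRF rule, and nothing is overridden. This stands in part. A reader might infer that the related-AE results will replace the collected data, but the documents do not support that as a certainty; it happens only if the blanket sentence is programmed over the eCRF rule. The reply does not rescue the sentence, however. As a description it misstates Protocol 6.2.5.2, and as an analysis rule it contradicts both that section and the SAP's own by-relationship paragraph.

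The second reply concerns reach. Relatedness does not enter the primary safety endpoint. The only endpoint that uses it concerns unsolicited AEs, and the overview shows solicited local, solicited systemic and related unsolicited AEs on separate rows. A subject also leaves the overview row only if every solicited reaction, injection-site reactions included, was judged unrelated and there was no related unsolicited AE. All of this stands and limits the effect.

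A reader might also infer that the blanket sentence turns every medically attended solicited reaction into a pausing event, because one criterion is "Occurrence of one or more SAE(s), MAAE(s), or PIMMC(s) judged to be related to IP". The documents do not require that. The criterion has the same wording in Protocol 3.1.3 and SAP 11.1 and turns on a judgement. Protocol 10.1.2 gives causality to the investigator or designee, and the blanket sentence sits in the analysis section without redefining that judgement. What remains is that the sentence could be read into the criterion, which is reason to align the texts.

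Finally, counting all solicited reactions as related leans the same way as the imputation of missing relationship. That could justify an all-related display, but not an undeclared one that conflicts with a stated rule.

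**Conclusion.** The point holds as a contradiction in wording with a conditional effect. SAP 9.1 conflicts with Protocol 6.2.5.2 and with its own by-relationship paragraph, and Section 13 does not declare a departure. If the blanket sentence prevails in programming, solicited reactions recorded as Unrelated are counted as Related in one overview row and one table, by dose and across doses, in all 12 groups.

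The size cannot be derived from the documents. The range of 0 to 16.2 points in the overview row rests entirely on the assumed rates above, and zero is a realistic end of it: that is the result if investigators record every solicited reaction as related. The primary safety result does not change under either rule.

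**What to change.** Delete the blanket sentence from SAP 9.1. State that relationship for solicited AEs is the investigator's eCRF value, in line with Protocol 6.2.5.2 and the by-relationship paragraph, and that this applies to the overview row as well as the table. The existing imputation of missing values can stay. If an all-related view is wanted, show it as a separate, labelled row and list it in Section 13 as a departure from the protocol.

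Reconcile Protocol 6.2.5.2, SAP 9.1 and the pausing rule in SAP 11.1, so that a related MAAE has one meaning throughout; which clinical rule applies is for the study's clinical team to settle.

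The cost is SAP wording, plus a program check that no derivation sets relationship to Related for non-missing solicited AEs. No new data are needed, because the assessment is already collected on the AE page.
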